4.4 Sample Size Considerations

The planned sample size is 75 randomized subjects per group for a total of 300 randomized subjects.

The mean and standard deviation for reduction in pain from baseline for placebo and active drug were estimated from publicly available sources on duloxetine, pregabalin, gabapentin, and oxycodone. The mean difference from placebo based on higher dose groups (duloxetine \geq 60 mg once daily and pregabalin \geq 300 mg) was estimated at 1.05. The standard deviation was estimated as 2.25.

A sample size of 75 subjects per group will provide approximately 80% power for a 2-sided t-test with Type I error of $0.05^{[5]}$ when the mean difference from placebo is 1.05 and the standard deviation is 2.25.

4.5 Study Design

The study will be a 6- to 9-week study, including a 1- to 4-week Screening Period, followed by a 4-week double-blind, parallel treatment, randomized, placebo-controlled Treatment Period, and a 1-week Follow-Up Period. The schedule of assessments is provided in in Appendix I.

4.6 Unblinding Study Drug Treatment Procedures

This is a double-blind study and therefore, the treatments assigned to each subject must remain blinded for analysis purposes until after database lock (not for safety concerns). Prior to database lock, this SAP will be signed off and considered final. After the electronic database has been locked, the treatment randomization codes will be unblinded and the analyses described in this SAP may be created.

4.7 Analyses Changes from the Protocol

In Section 9.2.5 of the protocol, 'moderate cases' (scores 11-15), and 'severe cases' (scores 16 or higher) were categories defined for Hospital Anxiety and Depression Scale (HADS) based on Zigmond 1983^[22]. However, more recent ranges are defined as 'moderate cases' (scores 11-14), and 'severe cases' (scores 15 or higher) based on Snaith 1994^[21].

In Section 12.4 of the protocol, it mentions that the modified Intent-to-Treat Population will be used for the efficacy analyses. This will be replaced with the Efficacy Population.

In Section 12.5 of the protocol, it mentions that treatment groups 200 mg combined with 50 mg of NYX-2925 will be provided in the summary tables. This specific grouping of multiple treatments will not be performed in this planned statistical analysis.

In Section 12.6.1.1 of the protocol, it states that study site will be used as a fixed factor in the analysis of covariance. Study site will not be included in the any statistical models due to low enrolling sites. Some study sites will not have all four treatment arms assigned to randomized subjects and this can affect some statistical models. The rest of the analyses stated in the protocol support the analyses planned in this SAP.

Section 12.8 of the protocol mentioned that a potential interim analysis would be conducted, but after additional consideration no formal interim analyses will actually be performed for this study. The sample size was calculated using a 0.048 Type I error, but the same results were based on a 0.05 Type I error without having an interim analysis.

5. General Statistical Principles

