12.5 Analyses of Efficacy

12.5.1 Primary Efficacy Endpoint

12.5.1.1 Primary Efficacy Analysis

For the primary efficacy endpoint, the daily pain intensity NRS score from the handheld device will be averaged for baseline (Days -7 to -1) and Week 4 (Days 22 to 28) after randomization. Change from baseline to Week 4 will be assessed for treatment group differences with an analysis of covariance with fixed factors for study site and treatment, with baseline value as a covariate.

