12.5.1.2 Sensitivity Analysis

For the primary efficacy endpoint, the daily pain intensity NRS score from the handheld device will be averaged for baseline (Days -7 to -1) and each week (Days 1 to 7, Days 8 to 14, Days 15 to 21, and Days 22 to 28) after randomization. A mixed model repeated measures analysis of variance will be used to assess treatment differences. The model will include factors for study site, treatment, week, and the treatment-by-week interaction, with baseline value as a covariate.

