4.2 Subject Randomization

At the Baseline visit, average daily pain scores and diary compliance will be transferred into the interactive response technology system, which will be used to assess the following criteria for randomization^[4]:

Eligible subjects will be randomized to receive either NYX-2925 10 mg daily, NYX-2925 50 mg daily, NYX-2925 200 mg daily, or placebo for 4 weeks in a 1:1:1:1 allocation. The randomization will be stratified by study site.

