5.3.5.3 Mixed Effects Repeated Measures Model

A mixed effects repeated measures (MMRM) model will be used for modeling analyses over time with each post-baseline analysis visit^[4]. The dependent variable will be the change from baseline and the model will include treatment (200 mg of NYX-2925, 50 mg of NYX-2925, 10 mg of NYX-2925, and Placebo), analysis visit, treatment-by-analysis visit interaction, the baseline value as a covariate, and subject as a random effect. The comparison of the NYX-2925 versus placebo will be assessed by forming the least squares means estimate of each particular NYX-2925 treatment groups stated in Section 5.2 and comparing them to the placebo group at each post-baseline analysis visit. An unstructured covariance structure will be used to model the within-subject errors. The Kenward-Roger approximation will be used to estimate denominator degrees of freedom. Here is the SAS® code:

PROC MIXED DATA=ADAM ORDER=DATA METHOD=REML;

CLASS USUBJID TRTP AVISITN:

MODEL CHG = BASE TRTP AVISITN TRTP*AVISITN / DDFM=KENWARDROGER;

REPEATED / TYPE=UN SUBJECT=USUBJID R;

LSMEANS TRTP*AVISITN / DIFF CL ALPHA=0.05;

RUN;

In case of convergence issues, other covariance structures will be used including (but not limited to) autoregressive (AR (1)), compound symmetry (CS), and variance components (VC) to find the covariance structure with the best fit. The fit statistics will be compared for all covariance structures; the structure with the smallest Akaike information criterion will be retained as the preferred model.

The following MMRM model statistics for each treatment group at every post-baseline analysis visit will be presented in an analysis table:

- n = the number of records for that treatment or pooled treatment group at that analysis visit
- Least Squares Mean for the treatment groups
- Standard Error for the treatment groups
- Least Squares Mean Difference for the NYX-2925 treatment groups versus Placebo
- Standard Error Difference for the treatment groups versus Placebo
- 95% Confidence Interval for the Difference for the treatment groups versus Placebo
- P-value for the Difference for the treatment groups versus Placebo

Each dependent variable and the particular analysis visit(s) will be described in the efficacy analyses Section 9 that will be used in a MMRM model.

5.3.5.4Time-to-Event Analyses

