5.7 By-Center Analyses

The study includes 39 study sites in the United States. Some study sites will not have all four treatment arms assigned to randomized subjects. Only the primary efficacy data described in Section 9.1 will be summarized using descriptive statistics by study site. No other by-center analyses will be planned in this SAP. Study site will not be included as a covariate in any statistical models.

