- 95% Confidence Interval for the Difference for the treatment groups versus Placebo
- P-value for the Difference for the treatment groups versus Placebo

Here is the SAS® code for Method 1:

RUN;

```
PROC MI DATA=ADAM NIMPUTE=5 SEED=8743216514 MINIMUM=0 MAXIMUM=10
OUT=ADAM_IMPUTE;
CLASS TRTP;
MCMC INITIAL = EM;
VAR TRTP BASE CHG1 -- CHG28;
RUN;
PROC MEANS;
BY _IMPUTATION_ AVISIT;
VAR CHG;
OUTPUT OUT=ADAM_IMPUTE_MEANS MEAN=CHG;
```

Protocol No.: NYX-2925-2001

```
ODS OUTPUT PARAMETERESTIMATES=MIXPARMS;

PROC MIXED DATA=ADAM_IMPUTE_MEANS ORDER=DATA METHOD=REML;

BY _IMPUTATION_;

CLASS TRTP;

MODEL CHG = BASE TRTP / DDFM=KENWARDROGER;

LSMEANS TRTP / DIFF CL ALPHA=0.05;

/* -1 = Placebo; 0 = 10 mg of NYX-2925; 0.5 = 200 mg and 50 mg of NYX-2925 */

LSMESTIMATE "200 mg and 50 mg of NYX-2925 versus Placebo" TRTP 0 0.5 0.5 -1 / CL;

RUN;

PROC MIANALYZE PARMS=MIXPARMS ALPHA=0.05 MULT;

CLASS TRTP;

MODELEFFECTS INTERCEPT TRTP;

RUN;
```

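### The SAP drops site, the only stratification factor, from the ANCOVA and MMRM for a reason that does not rule out a random site intercept; if sites differ, the test is slightly conservative

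*SAP*

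**What the plan says.** SAP 4.2 states: "The randomization will be stratified by study site". Protocol 12.2 says the same, and neither document names another stratification factor. Protocol 12.5.1.1 specifies for the primary endpoint an "analysis of covariance with fixed factors for study site and treatment, with baseline value as a covariate". For the MMRM, Protocol 12.5.1.2 states: "The model will include factors for study site, treatment, week, and the treatment-by-week interaction, with baseline value as a covariate".

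SAP 4.7 lists the removal of site as a departure from the protocol: "Study site will not be included in the any statistical models due to low enrolling sites". It explains: "Some study sites will not have all four treatment arms assigned to randomized subjects and this can affect some statistical models". SAP 5.7 repeats the decision: "Study site will not be included as a covariate in any statistical models".

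The code agrees. The ANCOVA in SAP 5.3.5.2 and its multiple-imputation version in SAP 9.1.3 use `MODEL CHG = BASE TRTP / DDFM=KENWARDROGER`, and the MMRM in SAP 5.3.5.3 uses `MODEL CHG = BASE TRTP AVISITN TRTP*AVISITN / DDFM=KENWARDROGER`. Site survives only as a grouping variable for descriptive statistics on the primary data (SAP 5.7). The SAP offers no pooling of small sites, no random site effect and no site-adjusted sensitivity analysis.

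**The concern.** Randomizing within site largely balances site differences out of the comparison between arms. A model without site leaves those differences in the residual variance, so the reported standard error describes a noisier comparison than the one the design produced. If sites differ in mean change, confidence intervals are somewhat too wide, the true type I error falls below 5%, and a little power is lost. If sites do not differ, nothing is lost. There is no bias and no inflation of false positives.

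The stated reason does not support the decision. A site that lacks an arm makes a full site-by-treatment model non-estimable, but neither document plans one. An additive site effect can still be fitted. A random site intercept also keeps every small or single-arm site in the analysis.

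The documents themselves treat site as possibly informative. Protocol 6.1 allows education to be repeated when pain-score variability rises at a site, and SAP 9.2.6 imputes missing baseline QOL-DN items from the mean at the same site.

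**Working it through.** **Inputs from the documents.** 75 subjects per arm and 300 in total, difference 1.05, SD 2.25 (SAP 4.4); two-sided alpha 0.05 (SAP 5.6); 1:1:1:1 allocation stratified by site (SAP 4.2); 39 sites (SAP 5.7), so 300/39 = 7.7 subjects per site on average.

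**Assumptions.** The documents give no between-site ICC, site-size pattern or block size. The ICC is taken as 0, 0.02, 0.05 and 0.10.

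**1. The planned power.** SE = 2.25 × √(2/75) = 0.367, and 1.05/0.367 = 2.858. Power is Φ(2.858 − 1.96) = 81.5%, or 81.0% by the noncentral t with 148 df. The stated figure of about 80% reproduces. It contains no site term.

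**2. Closed form under perfect within-site balance.** The no-site model reports an SE near 0.367. The true SD of the contrast is 0.367 × √(1 − ICC). Therefore:
- SE excess = 1/√(1 − ICC) − 1
- true type I error = 2Φ(−1.96/√(1 − ICC))
- power without site = Φ((2.858 − 1.96)/√(1 − ICC))
- power with site = Φ(2.858/√(1 − ICC) − 1.96)

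| ICC | SE excess | Type I error, no site | Power, no site | Power, with site | Gain (points) |
|---|---|---|---|---|---|
| 0.02 | 1.0% | 4.8% | 81.8% | 82.3% | 0.5 |
| 0.05 | 2.6% | 4.4% | 82.1% | 83.4% | 1.3 |
| 0.10 | 5.4% | 3.9% | 82.8% | 85.4% | 2.6 |

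**3. Simulation with uneven sites.** 39 sites with skewed enrolment, 300 subjects, site-stratified blocks of 4, total SD 2.25, a baseline covariate with no prognostic value, and 10,000 trials per ICC. On average 13 sites lacked an arm and 5 had only one.

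| ICC | 0 | 0.02 | 0.05 | 0.10 |
|---|---|---|---|---|
| No-site SE too large by | 0.5% | 0.8% | 1.8% | 4.7% |
| Type I error, no site | 4.7% | 5.0% | 4.7% | 3.9% |
| Power, no site | 81.0% | 82.0% | 81.9% | 82.3% |
| Power, random site intercept | 81.3% | 82.6% | 83.1% | 84.6% |
| Power, unpooled fixed sites | 79.4% | 80.4% | 81.7% | 83.7% |
| Power, fixed sites, those under 8 subjects pooled (assumed rule) | 80.9% | 82.1% | 82.7% | 83.8% |

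The random intercept gains 0.3, 0.6, 1.2 and 2.2 points over the no-site model. With blocks of 8 the gains are 0.2, 0.5, 1.1 and 2.2. Its type I error was 4.8% to 5.5% over all cases. Monte Carlo SE is about 0.2 points on type I error and 0.4 on power.

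**4. Separate simulation.** 4,000 trials per cell with the same layout gave type I error of 4.9 / 4.7 / 4.2 / 3.6% without site and 4.9 / 4.9 / 4.9 / 4.7% with a random intercept. Power gains were about 0.2 / 0.4 / 1.2 / 2.8 points.

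**5. Do missing arms prevent a site term?** In 500 simulated layouts about 12 sites on average lacked an arm, and the additive site-plus-treatment model had full rank in all 500.

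**Limits.** Residual degrees of freedom stood in for Kenward-Roger in the simulation of step 3. Dropout was not modelled. The MMRM was not simulated; the same reasoning applies to it.

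**The case against.** The strongest reply is that nothing is broken. The no-site test is valid, the change is declared with a reason, the SAP is to be final before database lock (SAP 4.6), and the planned power assumed no site term. All of that stands, and it keeps the severity low.

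The low-enrolment argument also has force against what the protocol specified. Unpooled fixed sites have lower power than the no-site model up to ICC 0.05 (81.7% against 81.9% there). The SAP was right not to keep that model, but the argument does not reach a random intercept.

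A sharper point is that the random intercept does not make the treatment estimate more precise. In 6,000 simulated trials per cell the empirical SD was 0.359 under both models at ICC 0.05 and 0.352 under both at ICC 0.10. This is correct. The gain comes from an SE and a test calibrated to the stratified design, and at equal actual type I error the power is the same within Monte Carlo error.

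The effects at ICC 0 and 0.02 are within noise. Monte Carlo error on an empirical SD from 10,000 trials is about 1/√20,000 = 0.7%, so SE excesses of 0.5% and 0.8% cannot be told from zero.

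The upper value of 5.5% for the random intercept's type I error raised a doubt about the remedy. The separate simulation, at 4.7% to 4.9%, does not bear it out.

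**Conclusion.** The concern holds, at low severity. Site is the only stratification factor, the SAP removes it from every model, and the reason given does not exclude a random site intercept. The consequence is mild conservatism if sites differ. It is negligible at ICC 0.02, about 1.2 points of power at 0.05, and about 2 to 3 points at 0.10, where type I error is 3.6% to 3.9% in place of 5%. If sites do not differ there is no loss. Which case applies is unknown, because the documents give no between-site variance. The sizes rest on the assumed ICC, site-size pattern and block size, and on a single-visit ANCOVA without dropout.

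**What to change.** Add a random site intercept (site in `CLASS`; `RANDOM INTERCEPT / SUBJECT=site`; Kenward-Roger kept) to the ANCOVA in SAP 5.3.5.2, to its multiple-imputation counterpart in SAP 9.1.3 and to the MMRM in SAP 5.3.5.3. Include no site-by-treatment term and no unpooled fixed site terms. Settle this before database lock, and report the no-site model as a sensitivity analysis.

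The secondary ANCOVAs take the change through the shared model in SAP 5.3.5.2, as do the analgesic-use subgroup models. This fits Protocol 12.5.2, which also had site in the secondary ANCOVAs. The Cox and chi-square analyses need no change, since the protocol did not put site there.

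The cost is a class variable and one line in each of three `PROC MIXED` calls, plus edits to SAP 4.7 and 5.7. The multiple-imputation code needs a little more. Its averaging step is by imputation and analysis visit only, so the site identifier must be carried through to the model. If the site variance is estimated as zero, the model reduces to the current one.

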5.1 Key Definitions

The following items below are standard terminologies discussed throughout the SAP.

5.1.1 Day 1/Date of First Dose

Day 1 is also referred to in the protocol and CRF as Visit 2, Baseline Visit, and Week 0.

The date of first dosing of study drug is not collected on the CRF because subjects are given study drug to administer themselves. Therefore, it will be assumed that Day 1 is the same day as the first dosing day of study drug for subjects in the safety population later described in the SAP in Section 6.1.

5.1.2 Study Day

Study day will be calculated in reference to Day 1 stated above in Section 5.1.1. For assessments conducted on or after the Day 1 date, study day is calculated as the assessment date – Day 1 date + 1. For assessments conducted before the Day 1 date, study day is calculated as the assessment date – Day 1 date. There is no Study Day 0 in this study.

5.1.3 Not Reported

A not reported value may be displayed in a listing, summary statistics table, frequency table, shift table, etc. The not reported record could be due to a missed sample/measurement/assessment, missed visit, unable to calculate a value, or withdrawal from the study early.

5.1.4 Baseline and Post-Baseline Values

Unless otherwise specified, the baseline value is defined as the last measurement/assessment collected/derived on Day 1 or screening. Unless otherwise specified, post-baseline values are defined as collected/derived measurements/assessments after Day 1.

For specific questionnaire assessments, missing responses on Day 1 will not be substituted for screening values for the baseline specific questionnaires. If the total score cannot be calculated at Day 1, then the screening visit will be used if the total score can be calculated at screening. If the total score cannot be calculated for both screening and Day 1 visits, then the latest individual values and subscale scores will be used for the baseline. All questions within a specific questionnaire will be paired together in an analysis visit for the baseline records.

5.1.5 Change from Baseline

If both post-baseline and baseline values are present/imputed, then change from baseline is defined as each post-baseline value – baseline value. Otherwise the change from baseline will not be reported.

5.1.6 Percent Change from Baseline

If the baseline value is not equal to zero or missing and the change from baseline value is present/imputed, then the percent change from baseline is defined as 100 x (change from baseline / baseline) and is rounded off to 1 number after the decimal point. Otherwise the percent change from baseline will not be reported.

5.2 Treatment Group Comparisons

The following treatment groups will be summarized in the statistical tables:

- 200 mg of NYX-2925
- 50 mg of NYX-2925
- 10 mg of NYX-2925
- All Doses of NYX-2925
- Placebo
- Not Randomized and Not Treated
 - o This will only be displayed for the analysis population table that presents subjects screened, but were not randomized and were not dispensed study drug.
- All Subjects
 - This will only be displayed for the analysis population, subject disposition, and demographics tables.

Efficacy data subject listings will be presented by the planned randomized treatment arm each subject was assigned to. All other subject listings will be presented by the actual treatment arm if they received study drug.

The following treatment group comparisons will be performed for efficacy:

- 200 mg of NYX-2925 versus Placebo
- 50 mg of NYX-2925 versus Placebo
- 200 mg combined with 50 mg of NYX-2925 versus Placebo
 - o This pooled treatment group will only be displayed for the primary efficacy endpoint.
- 10 mg of NYX-2925 versus Placebo

5.3 Conventions

All tables, figures, listings, and analyses stated in this SAP will be generated using SAS® software version 9.4 or later.

In the event for subjects screened more than once for the study, the latest data collected will be used for all tables, figures, listings, and analyses stated in this SAP. For example, a subject may have deemed a screen failure, but specific changes in the protocol amendment #3 for the inclusion and exclusion criteria may allow certain past screen-failed subjects to be enrolled in the study. More details are stated in Section 7.3.

5.3.1 Descriptive Statistics

Descriptive statistics (the number of subjects [n], mean, standard deviation [SD], median, minimum, maximum, and not reported) will be used to summarize continuous variables. Means will be presented to one more decimal place than the recorded data. Medians will be presented using the same number of decimal places as the recorded data unless the calculated median results in an additional decimal place ending in "5" (i.e. 5 & 7 = 6, 5 & 8 = 6.5, etc.). Standard deviations will be presented to two more decimal places than the recorded data. Minimum and maximum values will be presented using the same number of decimal places as the recorded data.

For data reporting 3 or more numbers after the decimal point (i.e. urinalysis specific gravity), the descriptive statistics for mean, standard deviation, median, minimum, and maximum will all be reported to the same precision as the data was collected. For data reporting 2 numbers after the decimal point, the descriptive statistics for standard deviation will be reported as 3 numbers after the decimal place (same as the mean).

5.3.2 Frequency Distributions

Frequency distributions (count [n], percentage of subjects [%], and not reported) will be used to summarize categorical or qualitative variables. In general, the denominator for the percentage calculation will be based upon the total number of subjects in the study population for the treatment groups for that particular time point assessment. Records that are missing or not done will be displayed as "Not Reported" and will not be factored into the percentage calculation, unless otherwise specified. Percentages will be presented to a maximum of one number after the decimal place.

5.3.3 Shift Tables

Shift tables (count [n], percentage of subjects [%], and not reported) will be used to summarize categorical or qualitative variables just like frequency distributions, but will also factor in a change in time. For this study, shift tables will include a shift from the baseline analysis visit to each post-baseline analysis visit. If a categorical value is missing or not done at baseline and/or at a post-baseline visit, "Not Reported" will be presented in the shift table. Only observed records at both

baseline and each post-baseline visit will be factored into the percentage calculation, unless otherwise specified. Percentages will be presented to a maximum of one number after the decimal place.

Planned shift tables in the SAP will be discussed in their respective data sections. Categorical values that will be presented in the shift tables will be pre-defined (i.e. "Low", "Normal", "High", and "Not Done").

5.3.4 Safety Data Statistical Inference

All safety data summaries will use descriptive statistics, frequency distributions, and/or shift tables. No formal statistical testing will be performed with the safety data.

